## 6.7. Field Test

The Study Director will make every effort to check the weather conditions ahead of time and only schedule the field study in good weather.

### Compliance Check

Within 48-72 hours prior to the test day, subjects will be contacted by telephone to assess their health and potential exposures to COVID-19; those that do not meet the CDC's screening criteria will be excluded. Subjects will be told what time to arrive at the Test Facility. They will be advised not to use scented soaps, shampoo, deodorant, perfumes, or cosmetics for the 24 hours immediately preceding the study, and to wash only with hot water and the unscented soap provided at the attractiveness test meeting. Additionally, subjects will be asked not to drink alcohol, smoke or chew tobacco, or engage in vigorous exercise for the 24 hours prior to each test. Female subjects will be reminded that a pregnancy test will be conducted prior to any treatment. Subjects will be asked to wear light, loose fitting clothing that fully covers their body.

### Subject Arrival

Subjects will be asked to arrive at the Test Facility at a specific time, 3-4 hours prior to the start of testing. This will allow time for registration, randomization and treatment before travel to the test site. The subjects will have a briefing and a compliance check. Subjects will be reminded that they are free to withdraw at any time and that they will be compensated for their participation up to the time of their withdrawal. They will also be reminded that they have the option to request that their data not be used.

Test subjects will be reminded not to engage in activities that could promote sweating and abrade the treated leg (e.g., rolling down pants, crossing legs), and to be careful when using the restroom to protect the treated leg.

Due to COVID-19, all study staff and subjects in attendance on test days will wear masks and where possible maintain 6 feet of social distancing. Masks may be removed during exposure periods to allow subjects to aspirate mosquitos. Staff and subjects will be required to have their temperature tested using an infrared thermometer. Subjects who fail to abide by social distancing and mask wearing provisions will be asked to leave and may be replaced.

A study staff member will orally verify each subject's compliance with the pre-test conditions on each test day prior to performing any treatment with a test substance. They will additionally check that eligibility criteria have not changed for example any new health conditions that may affect participation.

### Randomization for Assigning Test Subjects and Alternates

The first seven males and first seven females to arrive at the Test Facility will be selected as test subjects, plus the eighth male or female. The remaining subjects will be alternates.

The 15 selected test subjects will be randomized to either control or repellent treatment on the day of testing. To achieve this the RANDTREAT command will be used to generate a random allocation of six or seven treatments and a single control to the list of male and female participants (**Figure 2**). It will also be used to assign the treatment to the right or left leg (**Table 4**). The do-file for this will be pre-prepared, and run at the start of the test day when the participant list is finalised. On the test day, the Study Director will refer to this list, and assign the subjects to control or repellent treatment accordingly. For example, in **Table 4**, the third subject will be the control subject.

### Figure 2. Do File Example for randomisation in STATA

```
generate PPT_ID = .

[Manually write in 7/8 ID numbers for males/females]

splitsample, generate(TREATMENT) split(1,6) rseed (0)

[if 8 numbers, split (1,7)]

splitsample, generate(LEG) split(3,4) rseed (1)

[if 8 numbers split (4,4)]
```

**Table 4. Example STATA randomised dataset, where TREATMENT = 1 is control and 2 is repellent, and LEG = 1 is right leg and 2 is left leg.**

	PPT_ID	TREATMENT	LEG
1	121501	2	1
2	121502	2	1
3	121503	1	2
4	121504	2	1
5	121505	2	2
6	121506	2	2
7	121507	2	2

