## 7. Statistics and Data Analysis

### 7.1. Sample Size Calculation

EPA statisticians used a Weibull distribution to simulate the sample size required to estimate the median CPT to a given degree of precision. A power analysis of these outputs resulted in a sample size of 13 subjects being chosen. This number allows for over 90% power at a range of expected median CPTs from 2-8 hours (Appendix 4: Sample size calculation).

This sample size is appropriate to achieve at least 90% power that the ratio of 95% LCL mCPT/mCPT  $\geq$  0.6), given that the P5MR (i.e., CPT5th percentile/mCPT) is assumed to be equal or greater than 0.5. The assumption for the variation of CPT data distribution is characterized by the value of P5MR, associated with the selected sample size and the result of power. The P5MR value characterizes the spread of the CPT data distribution. For two products with same mCPT, the product with lower value of P5MR has a wider range of CPT data.

To maintain gender balance among the volunteers, at least 6 volunteers of each sex will be recruited to test each product. An additional 2 subjects will be required to act as untreated controls. Five alternate subjects will be invited to take part in each study day. Subjects will be able to take part in one or both test days. Therefore, a minimum of 20, and a maximum of 40 subjects will be required to complete the trial.

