### **8.7. Data Management**

Informed consent forms will contain the subjects' full names. The subjects' names will be entered onto an enrollment log and each subject will be assigned a subject identification number. All other data collection forms will use the subject identification number only (see Appendix 8).

During screening the subject will self-complete an eligibility questionnaire including their date of birth and some medical history. All other data collected will be recorded in the case report form (CRF) and signed on each page by the researcher responsible. The CRF is considered to be source data. Data to be collected on the CRF are: subject number a date of test on every page, confirmation of informed consent, eligibility details, attractiveness test data (number of mosquitos attracted to arm); training data (successful attempts to capture mosquitos); leg measurements; test visit data (product application details, mosquitos caught, times of testing); and adverse event monitoring.

Raw data from the CRF will be entered into a database, from which datasets can be extracted for analysis. This database and any datasheets or analysis produced will be saved in a location with access limited by password identification to members of the study team. Data will be double entered and verified to ensure accuracy. The Study Director will confirm that all data from all subjects have been entered to avoid analysing an incomplete data set. CRFs will be kept in secure storage after completion. Information in the database will be linked to a relevant SOP, risk assessment, contract, and files of statistical analysis and location of study report.

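### Do the constant seeds, hand-typed IDs and mismatched command names in the example randomization code put the control allocation at risk?

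*Protocol*

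**What the plan says.** Under Randomization for Assigning Test Subjects and Alternates (Protocol, section 6.7), 15 subjects are chosen by order of arrival: seven of each sex plus one more of either sex. Each test day therefore has one list of 7 and one of 8. For the allocation, "To achieve this the RANDTREAT command will be used to generate a random allocation of six or seven treatments and a single control" within each list, and the same command assigns the leg. On timing, "The do-file for this will be pre-prepared, and run at the start of the test day when the participant list is finalised".

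Figure 2, headed "Do File Example for randomisation in STATA", shows the code. Its first instruction is an editorial note, "Manually write in 7/8 ID numbers for males/females". Treatment is then set by "splitsample, generate(TREATMENT) split(1,6) rseed (0") and leg by "splitsample, generate(LEG) split(3,4) rseed (1"). For a list of 8 the notes change the split sizes only. Table 4, also labelled an example, shows seven IDs in ascending order with the third as control. The Protocol has no text on how the real seed is chosen, whether it differs by sex or day, or in what order IDs are entered.

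**The concern.** A random-number command with a constant seed and a fixed list length returns the same answer every time. If the printed seeds were kept, the control's row in each list could be known before anyone arrived. Whoever types the IDs could then decide who fills that row.

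Staff would have something to act on. The case report form holds "attractiveness test data (number of mosquitos attracted to arm") before the test day. Section 7.1 adds "Subjects will be able to take part in one or both test days", so a day-1 result on the other product may also be known. The allocation decides which 2 of 15 people are left out of the 13 who give the median CPT. Making a likely early failure a control would lengthen the estimate that supports the product's efficacy claim. In addition, text and code name different commands for the same step, which is untidy in a study run under Good Laboratory Practice.

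**Working it through.** 1. **Do the printed splits give the stated numbers?** The inputs are split(1,6) for the list of 7 and split(1,7) for the list of 8 (Figure 2). Controls: 1 + 1 = 2. Treated: 6 + 7 = 13. Total: 15. This matches sections 3 and 6.7. Table 4 has 1 control and 6 treated, with 3 right and 4 left legs, as split(1,6) and split(3,4) require. The difference in command name does not alter the group sizes.

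2. **What does a constant seed do?** A random-sort split in Python, standing in for the Stata command, gave 1 distinct control row in 10,000 runs at seed 0, for n = 7 and again for n = 8. With varying seeds every row occurred, at frequencies of 0.139 to 0.146 (expected 1/7 = 0.143) and 0.121 to 0.128 (expected 1/8 = 0.125). The chance that both control rows repeat on day 2 is 1 with constant seeds and 1/7 × 1/8 = 1/56 = 0.018 with fresh ones. This shows the principle but not which row Stata would pick.

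3. **Is a repeated row a repeated person?** Only if the same person is typed into that row. Lists form by arrival on the day, and section 7.1 allows 20 to 40 different people over the two days. If the ID order does not depend on what staff know about the subjects, a known row selects nobody in particular.

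4. **How far could the estimate move if someone did steer?** The Protocol gives no figure for this, so assumptions are needed. CPT is taken as Weibull, as in Appendix 4, with shape k = ln[ln(1/0.95)/ln 2] / ln(P5MR), where P5MR is the 5th percentile divided by the median. The numerator is ln(0.0513/0.6931) = −2.604, so k = 3.76 at P5MR 0.5 and 7.30 at P5MR 0.7. The advance information is a normal score with correlation ρ to the CPT score. The lowest scorer in each list becomes control, instead of a random member. The outcome is the 7th ordered time of the 13 treated, which is the Kaplan-Meier median without censoring. Mean shift in hours over 200,000 simulated sets per scenario (Monte Carlo standard error at most 0.001 h):

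| P5MR | Median (h) | ρ = 0 | ρ = 0.3 | ρ = 0.5 | ρ = 1 |
|---|---|---|---|---|---|
| 0.5 | 6 | 0.00 | +0.116 | +0.187 | +0.303 |
| 0.5 | 8 | 0.00 | +0.155 | +0.252 | +0.402 |
| 0.7 | 6 | 0.00 | +0.059 | +0.096 | +0.156 |
| 0.7 | 8 | 0.00 | +0.080 | +0.129 | +0.207 |

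With only the list of 7 steered, at ρ = 0.3 and P5MR 0.5, the shift is +0.056 h (6 h) or +0.075 h (8 h). At ρ = 0.3 with both lists steered the range is 0.059 × 60 = 3.5 minutes to 0.155 × 60 = 9.3 minutes. The ceiling is 0.402 × 60 = 24 minutes. Exposures are 30 minutes apart.

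5. **Is there support for a nonzero ρ?** The attraction test (section 6.2) counts landings on an untreated arm in a cage of *Aedes aegypti*, and everyone kept in the study has passed its threshold. Nothing in the Protocol links that count to protection time on a treated leg against mixed field species. A day-1 CPT exists only for people who return.

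**The case for a change.** The strongest case for a change is that Figure 2 is the only allocation code in the Protocol. Its bracketed notes mark the IDs and split sizes as items to adjust, but not the seeds. A reader could reasonably carry 0 and 1 into the real do-file, which is written before the list exists. Advance information of some kind is on file, the study supports a label claim, and two sentences would remove the question.

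Part of this stands. The two command names do disagree, the text is silent on seed and entry order, and a seed known before an unordered list is typed is weaker than it needs to be.

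Three points limit it. First, the bracketed prose means the code cannot run as printed, so an operational do-file has to be written anyway, and 0 and 1 read naturally as placeholders. Second, a seed written down in advance makes the allocation reproducible: with the saved list, an auditor can re-run it and see the entry order. Third, the obvious remedy, drawing a fresh seed on the day once the IDs are known, is not clearly safer. Unless someone independent draws it, it allows redrawing until a preferred control comes up. Entering IDs in a fixed order with a pre-recorded seed would close the same route, and nothing in the Protocol stops staff from working that way.

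**Conclusion.** No change to the plan is needed. RANDTREAT against splitsample is a clerical mismatch: the printed splits deliver the stated 13 treated and 2 controls. Seed choice and entry order are operational details that a competent team settles in the working do-file and study records.

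The plan's inference does not depend on them. The primary estimate is a Kaplan-Meier median in treated subjects, the two controls only gauge landing pressure, and no treated-versus-control contrast could be biased. The 1 against 1/56 figure describes list rows, not people.

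Any shift in median CPT requires the real do-file to keep the printed seeds, someone to reorder IDs on purpose, and advance information that predicts CPT. If any of these is absent the shift is 0. If all hold, at an assumed correlation of 0.3, it is +0.06 to +0.16 h for medians of 6 to 8 h and P5MR of 0.5 to 0.7. The ceiling under perfect foresight is +0.40 h. These are mean shifts under a Weibull model, and the correlation is an assumption without support in the Protocol.

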### Pregnancy Test

Female subjects will be asked to conduct a pregnancy test prior to any treatment, as described above. All efforts will be taken to maintain the confidentiality of the pregnancy test results. The results will not be disclosed to anyone other than the test participant, the verifying employee, and/or Study Director.

### Repellent Application

The lower leg to be treated (or left untreated for control subjects) will be washed with unscented soap and water, rinsed with isopropyl alcohol (70% in water) and dried with paper towels.

The dose required for each subject will have already been calculated, checked and recorded in their case report form following the participant's leg measurements being taken. This dose will be measured and applied evenly over the lower leg from the ankle to the knee using a single gloved finger to ensure uniform coverage. The AKIVA 20 Lotion dose will be measured directly by weight, but the AKIVA 20 wipe will be wrung out first and a measured weight of the liquid applied.

- For the lotion, a spatula will be labelled with the participant ID and placed on the balance, and the balance tared. The required weight of the test substance will then be added to the spatula. Then the product will be applied to the subject using a gloved finger directly from the spatula. The spatula will be reweighed until it contains less than 0.05 g product.
- For the wipe, a beaker will be placed on the balance and the weight recorded. One to two wipes will be squeezed into the beaker and the weight recorded. The beaker will be labelled with the participant ID and the excess product will be removed from the beaker using a spatula. Then the product will be applied to the subject using a gloved finger directly from the beaker. The beaker will be reweighed until it contains less than 0.05 g product. The excess product that is removed will be weighed and recorded as "disposed" in the product accountability log.

Due to the number of test subjects requiring repellent application, more than one trained technician may apply the test substances to subject's legs. Technicians will ensure consistency as best as possible. The time of application will be recorded for each subject on their case report form.

#### **Transport to and from the Field Site**

Subjects will be transported to the field site by the study staff and will be returned to the Test Facility at the end of the testing day. Subjects may also drive in their own vehicles if they wish. In order to maintain the integrity of the treatment, subjects will again be reminded to avoid abrading, rubbing, touching or wetting the treated area. Multiple vehicles will be used to ensure that subjects can remain at an appropriate social distance as far as possible.

If a subject experiences product failure before the end of the full test day they will remain with the group until the next vehicle is available to return them to the Test Facility.

#### **Randomization for Human Landing Catches**

Nine collection stations ('A'-I') will be set up at the field site, with a minimum distance of 3 meters between each station. Subjects will be paired and assigned to the collection stations according to a randomization procedure.

Control and repellent treated individuals will not be paired together to avoid diversion of landing to control subjects. Additionally, difference in attractiveness can result in diversion of landing from one control to another. Therefore, the two controls will not be paired together, but with study staff. Study staff will perform counts, but will not expose their own legs. Unpaired test subjects will also be assigned a staff member in the same manner.

To achieve the randomization, first, the initials of three staff members will be listed in a column in a STATA dataset (**Table 5**, column B), alongside a column in which random numbers are generated (column C). The two lists will be ‘sorted’ according to the random number list, from smallest to largest. The first staff member will make a pair with the female control subject, the second with the male control subject, and the third with a treated subject (column A).

To determine the pairings, another dataset will be prepared in which the third staff member and the participant IDs of the 13 treated subjects are listed in a column (**Table 5**, column E), alongside a column in which a random number will be generated (column F). The two lists will be ‘sorted’ according to the random number list, from smallest to largest. The first two individuals in the list will make test pair 1, the second two individuals will make test pair 2, etc. (column D). The eighth pair will be the male control pairing and the ninth pair will be the female control pairing. The pairs will not change throughout the test day. Test pairings will be assigned to test stations through a Latin square design (see Appendix 3).

A record of which subjects were paired together and where they were positioned throughout testing will be maintained to facilitate contact tracing, if necessary.

**Table 5. Example randomization of subject pairings.**

A	B	C	D	E	F
Pairing	Staff member initials	Random number	Test pair	Participant ID/ staff initials	Random number
Female control	TJ	0.1329	1	215021	0.0518
Male control	CH	0.2691	1	LC	0.0691
Treated	LC	0.5786	2	215034	0.1139
			2	215022	0.3075
			3	215064	0.5146
			3	215007	0.5797
			4	215013	0.6217
			4	215018	0.6599
			5	215024	0.6745
			5	215044	0.7217
			6	215049	0.7448
			6	215077	0.8894
			7	215003	0.9544
			7	215050	0.9646

### Human Landing Catches

Human landing collections will start 2 hours after product application. Other products registered with the EPA that contain 20% IR3535, have been shown to give a similar level of protection to 10% DEET. In addition, these test products were previously tested in field sites in Florida, and the EPA allowed data from those studies to support a claim of 3 hours complete protection. Therefore, it is highly unlikely the test products will fail within this time delay. The 2-hour time delay will allow repellent application to be carried out at the test facility where measuring equipment can be kept calibrated and in good condition, before travelling to the field site to start collections.

A minimum of three consecutive exposure periods should occur before subjects experience a first confirmed landing. If a first confirmed landing occurs within the first three exposure periods, the CPT will be counted as 0 hours. Subjects experiencing a first confirmed landing at two hours post application or within the first three consecutive exposure periods should not be replaced.

The mosquito landing pressure will be determined before the treated volunteers expose their legs. Control subjects will expose their lower leg for 5 minutes or until 5 landings occur, whichever is sooner. As soon as 5 landings occur, regardless of whether 5 minutes have elapsed, the control subject can cover the lower leg to minimize the potential for mosquito bites. Landing pressure will be assessed for each 30 minute interval. The time of the landings and when the threshold number of landings occur will be recorded. If the landing pressure is insufficient, test subjects will carry out their exposures in that time period unless the total number of exposure periods with low landing pressure exceeds three consecutive periods or four non-consecutive periods with inadequate landings on controls, and the test should be stopped.

The treated lower limb of the test subjects will be exposed for 5 consecutive minutes, during each 30 minute interval for the trial period. Under supervision of a trained member of staff or another subject, the number and timing of each landing during each exposure period for each subject will be recorded.

All insects landing on the treated and control subjects' exposed lower legs will be collected by aspiration (before they have chance to probe or bite) and labelled with the subject number, treatment status, date and time of collection. Mosquitos will be identified to genus or species as appropriate. Then samples will be pooled by subject and date and tested for pathogen prevalence as appropriate. Mosquitos landing elsewhere on the body will not be collected.

Human landing collections for each subject will continue until treatment failure. Treatment failure is defined as one mosquito landing followed by a confirmatory landing either in the same 5 minute exposure period, or in the following exposure period. If treatment failure is reached in more than half of subjects, all other subjects will also stop testing and the test will be concluded. If treatment failure is not reached in more than half of subjects, the test will continue until 14 hours post application for the lotion, or 13 hours for the wipe. A median CPT can be established when there is time to treatment failure data for half the subjects, so at this point there is no need to risk exposure of subjects who have not reached treatment failure.

Between exposure periods all subjects will have access to restroom facilities, and a shaded, screened location with adequate seating. In addition, subjects will have access to cold drinks (water, soft drinks, etc.) and snacks to keep them hydrated and to maintain their blood sugar. Subjects may also consume their own food or drinks they bring; read, or engage in other leisure activities. Test subjects will be reminded not to engage in activities that could abrade the treated leg and to be careful when using the restroom to protect the treated leg.

